Title: Regional Blockade of the Sternum with Liposomal Bupivacaine Prior to Incision Decreases Opioid Use in Patients undergoing Cardiac Surgery

Personnel:

- a) Principal Investigator: [name]
- b) Sub-Investigators:
 - i) [name]
 - ii) [name]
 - iii) [name]
 - iv) [name]
 - v) J. [name]
 - vi) [name]
 - vii) [name]
 - viii) [name]
 - ix) [name]
 - x) [name]
 - xi) [name]
 - xii) [name]

Background:

Prolonged and excessive narcotic usage in the postoperative setting has been linked to multiple complications. Use of complimentary pain management techniques such as regional analgesia can reduce postoperative pain and narcotic usage. This can enhance patient recovery and improve quality of life in the immediate postoperative period. [1] Previous research investigating the benefits of local analgesia during cardiac surgery have been limited by the sparse amount of single-center randomized controlled trials, particularly evaluating the use of para-sternal injections.

Of the available studies, the use of local analgesia injections compared to controls has led to improved pain scores and overall decreased perioperative opioid usage. Studies have shown this efficacy using 0.2% ropivacaine, [2] 0.75% ropivacaine, [3] and 0.53% liposomal bupivacaine [4] all compared to control groups receiving normal saline injections in the para-sternal area. These studies all used injections just prior to sternal closure and no significant evidence is available for the use of ultrasound-guided regional block of the sternum prior to surgical incision. Injection of analgesia prior to surgical incision has been shown to decrease postoperative pain compared to injection after surgical closure. [5]

Hypothesis/Aims:

We hypothesize that injection of 1.3% liposomal bupivacaine and 0.5% bupivacaine (20mL dose) as a sternal block prior to surgical incision will lead to decreased pain and opioid usage in the intraoperative and postoperative setting for patients undergoing upper mini- and median sternotomy compared to controls (normal saline block).

Aim 1: To demonstrate decreased postoperative opioid usage and decreased pain scores in the postoperative setting in the treatment group compared to controls.

The amount of opioid medications used will be recorded during the routine postoperative course. Pain scores, set by a validated system, will be obtained daily during the routine postoperative course.

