4. ICU LOS
5. Total LOS from date of sternotomy
6. Return of bowel function
7. Postoperative atrial fibrillation

8. Maximum spirometry at 24, 48, 72 hours post op
9. CAM at 24, 48, 72 hours post op
10. Pain Scores (Scale 0-10) at 1, 2, 4, 8, 12, 24, 36, 48, 60, and 72 hours after ICU arrival for extubated patients and CPOT scores (Scale 0-8) for intubated patients
11. Post op opioid usage up to 72 hours post op

Standard descriptive statistics will be used throughout (mean, range, standard deviation, and median, IQR), with comparative statistics for normally and non-normally distributed data with $p < 0.05$ considered as significant. For categorical variables, 2 Sample t-test or chi-squared test will be used to determine statistical significance. For continuous variables, logistic regression will be used to determine the value of significance to variables with postoperative outcomes. Depending on the enrollment rate, the stratification of data based on the type of sternotomy (full or mini) could be performed and analyzed respectively.

References

1. Bignami, E., et al., *Perioperative pain management in cardiac surgery: a systematic review*. Minerva Anestesiol, 2018. 84(4): p. 488-503.
2. Dowling, R., et al., *Improved pain control after cardiac surgery: results of a randomized, double-blind, clinical trial*. J Thorac Cardiovasc Surg, 2003. 126(5): p. 1271-8.
3. Barr, A.M., E. Tutungi, and A.A. Almeida, *Parasternal intercostal block with ropivacaine for pain management after cardiac surgery: a double-blind, randomized, controlled trial*. J Cardiothorac Vasc Anesth, 2007. 21(4): p. 547-53.
4. Lee, C.Y., et al., *A Randomized Controlled Trial of Liposomal Bupivacaine Parasternal Intercostal Block for Sternotomy*. Ann Thorac Surg, 2019. 107(1): p. 128-134.
5. Labrum, J.T.t. and A.M. Ilyas, *Preemptive Analgesia in Thumb Basal Joint Arthroplasty: Immediate Postoperative Pain with Preincision versus Postincision Local Anesthesia*. J Hand Microsurg, 2017. 9(2): p. 80-83.

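### Aim 1 includes decreased pain, but the plan lists ten pain readings per patient at p < 0.05 and names no single pain comparison, repeated-measures method or multiplicity rule

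*Combined protocol and SAP*

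**What the plan says.** Under Hypothesis/Aims, Aim 1 is "To demonstrate decreased postoperative opioid usage and decreased pain scores in the postoperative setting in the treatment group compared to controls". The text below it adds: "Pain scores, set by a validated system, will be obtained daily during the routine postoperative course".

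The Postoperative Variables lists, under both Data elements and Data Analytic Methods, give a different schedule: "Pain Scores (Scale 0-10) at 1, 2, 4, 8, 12, 24, 36, 48, 60, and 72 hours after ICU arrival for extubated patients", together with "CPOT scores (Scale 0-8) for intubated patients".

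The inferential text is the closing paragraph of Data Analytic Methods:
- It promises "comparative statistics for normally and non-normally distributed data with $p < 0.05$ considered as significant".
- It continues: "For categorical variables, 2 Sample t-test or chi-squared test will be used to determine statistical significance".
- It assigns logistic regression to continuous variables.

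Narcotic usage is treated differently: its between-group difference is to be reported as one value. Pain has no equivalent statement.

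**The concern.** Aim 1 asks one question about pain over the postoperative course, and the data are ten correlated readings on each patient. Nothing in the plan turns those readings into one answer. There is no mean, area under the curve, primary time, longitudinal model or rule for multiple tests. An analyst who follows the text could compare the arms at every time and report whichever reading falls below 0.05.

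Two things are at stake. A claim of decreased pain would carry a false-positive risk well above the nominal level. The information from repeated scoring would also go unused, in a trial of 150 patients for which no power, effect size or SD is stated.

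The two scales add a difficulty. Which scale applies depends on whether the patient is still intubated. That state arises after randomisation, and time to extubation is itself an Aim 3 outcome.

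**Working it through.** **Inputs from the documents.** Ten reading times (1, 2, 4, 8, 12, 24, 36, 48, 60, 72 h); threshold 0.05; 150 patients randomised 1:1, hence 75 per arm. The plan gives no figure for the pain analysis that could be reproduced.

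**Assumptions, not in the documents.** Two-sided tests; within-patient correlation ρ of 0.3, 0.5 or 0.7, either exchangeable (the same for every pair) or serial (ρ to the power of the number of readings apart); no missing readings; a treatment effect of 0.35 SD for the main power figures.

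**Step 1: false-positive chance if each reading is tested.** With independent readings, the chance of at least one p < 0.05 is 1 − 0.95^10 = 40.1%. Counting only results that favour the block, it is 1 − 0.975^10 = 22.4%. Readings on one patient are correlated, so these are benchmarks only. Simulating ten correlated standard-normal test statistics with no treatment effect (1,000,000 draws per scenario) gives:

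| Correlation | Either direction (nominal 5%) | Favouring the block (nominal 2.5%) |
|---|---|---|
| Exchangeable 0.3 | 35% | 18% |
| Exchangeable 0.5 | 29% | 14% |
| Exchangeable 0.7 | 21% | 11% |
| Serial 0.3 | 39% | 21% |
| Serial 0.5 | 36% | 19% |
| Serial 0.7 | 30% | 15% |

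The right-hand column is the one that bears on a claim of decreased pain.

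**Step 2: weights for a single summary.** The trapezoidal rule over 1-72 h gives the ten times weights of 0.5, 1.5, 3, 4, 8, 12, 12, 12, 12 and 6, which sum to 71. The first five readings carry 17/71 = 24% of the weight. In a plain mean they would carry 5/10 = 50%, because five of the ten times fall in the first 12 h.

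**Step 3: power when the effect is constant.** With exchangeable correlation, the variance of the weighted mean relative to one reading is ρ + (1 − ρ)·Σw². Here Σw² = 0.1396, which gives 0.398, 0.570 and 0.742 for ρ = 0.3, 0.5 and 0.7. Power comes from the noncentral t distribution with 148 degrees of freedom and noncentrality (d/√variance)·√(75/2):

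| Constant effect d (SD) | One reading | Weighted mean, ρ = 0.3 / 0.5 / 0.7 |
|---|---|---|
| 0.30 | 45% | 82% / 68% / 56% |
| 0.35 | 57% | 92% / 81% / 70% |
| 0.40 | 68% | 97% / 90% / 81% |

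**Step 4: power when the effect is short-lived.** Suppose 0.35 SD applies through 24 h and nothing after. The first six weights sum to 29/71 = 0.408, so the effect on the weighted mean is 0.35 × 0.408 = 0.143 SD. Power is then 28%, 21% and 17% for exchangeable ρ = 0.3, 0.5 and 0.7. A single reading inside that window keeps 57%.

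**The case against.** The strongest reply is that the plan never says it will run ten tests. The readings form one numbered variable, and no rule makes one significant reading a success. That is correct. A reader might infer that the plan prescribes ten tests and treats any one as proof of Aim 1, but the documents support only the weaker statement that nothing prevents it. A reader might also conclude that each time point is underpowered. No target effect is stated, so the documents cannot show that either.

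It can also be said that the either-direction figures overstate the matter, because they count results showing worse pain. This stands: the error relevant to Aim 1 is about half as large, though still several times its nominal level. Aim 1 also couples pain with opioid use, and requiring both would make a false joint claim rarer. The plan sets no such requirement, and if opioid use truly fell, the pain half would keep the error shown above.

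The methods paragraph is not confined to two-group tests, since it names logistic regression and unspecified comparative statistics. None of these combines repeated readings. The tests are also matched to the wrong variable types (a t-test for categorical data, logistic regression for continuous data), so no usable test for a pain score is clearly specified even at one time.

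Finally, one average is not the only way to control the error, and Step 4 shows it can do badly. A single primary time or adjusted tests would also be valid. The average is preferred because Aim 1 concerns the postoperative course and the Regional Block text cites prolonged analgesia.

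**Conclusion.** The concern holds as an omission: a named Aim 1 outcome has ten readings, a blanket 0.05 threshold, and no prespecified comparison to carry the claim. If each reading were tested, the chance of a false result favouring the block would be about 11-18% with exchangeable correlation (0.7-0.3) or 15-21% with serial correlation, against 2.5%. In either direction it would be 21-39% against 5%. The correlations are assumed, but the inflation appears in every scenario tried.

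The advantage of a single summary is conditional. At 0.35 SD with exchangeable correlation, power is 70-92% if the effect is constant and 17-28% if it ends at 24 h, against 57% for one reading taken while the effect is present. This should be corrected, cheaply, before any unblinded analysis. Spirometry at 24, 48 and 72 h belongs to Aim 3 and is a lesser instance.

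**What to change.** Amend Data Analytic Methods as follows.

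1. **One pain contrast.** Fit a mixed model to the 0-10 scores with arm, categorical time, arm-by-time and within-patient correlation. Test only the between-arm difference in the time-weighted (trapezoidal) mean over 1-72 h, and report it with a 95% CI.
2. **Profile.** Show the ten time-specific differences with intervals and no p-values.
3. **Intubated readings.** Report CPOT separately by arm and do not pool it with the 0-10 scale. State how times without a 0-10 score because of intubation enter the model. Add a sensitivity analysis, for example the same contrast from a later prespecified start time, because extubation time may depend on arm.
4. **Schedule.** Reconcile the daily pain scoring described under Aim 1 with the ten listed times.
5. **Spirometry.** The three readings can be handled in the same way, as a secondary outcome.

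The cost is SAP wording and a standard model on data already scheduled, plus the work of settling the CPOT rule. The main drawback is dilution of a brief effect. The profile would show such an effect but would not test it, so if early analgesia is the real target, a shorter window should be named in advance.

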Aim 2: To demonstrate decreased intraoperative opioid usage in the treatment group compared to controls

Aim 3: To demonstrate improvement in key clinical components closely linked to narcotic usage.

Multiple variables specific to opioid usage will be recorded during the routine postoperative setting. These included, but are not limited to: time to extubation, incentive spirometer volume, return of bowel function, postoperative atrial fibrillation incidence, delirium and intensive care unit (ICU) and overall lengths of stay (LOS).

Methods

This is an investigator-initiated prospective randomized study with an 18-month patient accrual period and patient follow-up period dependent on postoperative length of stay following surgery.

Regional Block: Liposomal Bupivacaine (1.3%) solution (20 mL dose) is proposed for use during this study. This solution has demonstrated increased efficacy in prolonged analgesia following injection. This solution will be injected as an ultrasound-guided subpectoral interfacial plane block.

Normal Saline: Normal saline (0.9%) will be used as the control solution for patients not receiving the liposomal bupivacaine solution. Injection procedure of this solution will be identical to that of the liposomal bupivacaine solution.

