Procedures: Patients undergoing a surgical procedure through mini- or full sternotomy will be considered for inclusion in this study. Qualified patients will be randomized 1:1 to a liposomal bupivacaine sternal block or a normal saline block. An unblinded research coordinator will use a password-protected spreadsheet to randomly generate the subject's randomization assignment. The unblinded coordinator will communicate the information to the unblinded anesthesiologist who will perform the block. This ensures the intraoperative (including a blinded anesthesiologist and surgeon) and postoperative staff (including the blinded research coordinator) will remain blind to the randomization assignment. The subject will also be blinded to the assignment. The amount of opioid medications given by the anesthesia team during the procedure will be recorded. Anesthesiologists will be encouraged to standard of care early extubation. There will be no deviation from routine surgical procedures following injection of para-sternal solution prior to surgical incision. Patients are considered part of the research study until they are discharged. After discharge, patients can be told which block they were given and the blinded coordinator can be unblinded to review all medical records.

Study Population

Patients undergoing a surgical procedure through mini- or full sternotomy from 7/1/2019 at THHBP will be included in this data set. A total of 150 patients is proposed for this study.

Inclusion Criteria:

1. Age greater than 18 years
2. Undergoing a surgical procedure through mini- or full sternotomy.

Exclusion Criteria:

1. Clinical instability

2. Allergic to liposomal bupivacaine solution or any of its ingredients
3. Maximum-allowed dosage of local analgesia will be exceeded by the injection amount of liposomal bupivacaine used in this study (<50 kg).

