7. HTN
8. HDL
9. Ethnicity (Hispanic & not Hispanic)
10. Race (Caucasian, African Americans, Asians and others)

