11. CKD
12. CVA
13. Chronic home NSAID use (excluding ASA)

Intraoperative Variables:

1. Type of procedure being performed
2. Prior procedures performed

Postoperative Variables:

Time to extubation, time to ambulation, time to oral diet, return of bowel function (bowel movement), postoperative atrial fibrillation incidence (through discharge), and intensive care unit (ICU) length of stay (LOS) and overall LOS. Maximum incentive spirometer maximum volume at 24, 48 and 72 hours, Confusion assessment method (CAM) at 24, 48 and 72 hours, post op opioid usage up to 72 hours post op. If additional days of post-op opioid usage is documented in the existing medical record, this may be used also. CAMs are performed by the blinded research coordinator.

Pain scores (Scale 0-10) at 1, 2, 4, 8, 12, 24, 36, 48, 60, and 72 hours after ICU arrival for extubated patients and CPOT scores (Scale 0-8) for intubated patients

Adverse Events: Allergic reaction, pneumothorax, pericardial tamponade, vascular injury, hematoma, intravascular injection, wound infection, paresthesia, persistent numbness. These adverse events will be monitored and reported from the start of the study procedure to discharge (study termination).

Protocol Deviations: If certain data elements are not in the existing medical record and were not collected, this is not a protocol deviation. Nevertheless, all effort will be made to collect these data points.

Funding: CVRRC

Journals in which you plan to publish or meetings where abstracts will be submitted: TBD

Risks and Benefits

Risks: The risks are the same as the Standard of Care surgery performed outside this study. This is discussed in the ICF. A confidentiality breach is a risk associated with research. However, all data collection protocols follow HIPAA guidance.

Benefits: If participants receive the drug, they could experience less pain than those that don't receive the drug. However, not all participants are likely to benefit from the proposed research. The investigators will benefit from the knowledge gained, as it will provide deepened insight on the main challenges, advantages and disadvantages of the procedure.

Data Analytic Methods

The mean, standard deviation, median, and interquartile ranges of narcotic usage (in morphine equivalent units) will be reported for each group. The difference of narcotic usage between the two groups will be reported as a single value. Additional variables analyzed in this study include the following:

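### Read by outcome type, the plan gives opioid amount a method that cannot compare the arms, and it does not define the between-arm difference to be reported

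*Combined protocol and SAP*

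**What the plan says.** The relevant text is all in the combined protocol and SAP.

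- **Data Analytic Methods, closing paragraph**, on choice of method: "For categorical variables, 2 Sample t-test or chi-squared test will be used to determine statistical significance. For continuous variables, logistic regression will be used". The rest of the logistic sentence speaks of relating variables to postoperative outcomes and names no dependent variable. Just before it, the paragraph promises "comparative statistics for normally and non-normally distributed data" at a 0.05 threshold. It gives no test, no rule for choosing between tests and no sidedness.
- **Data Analytic Methods, opening paragraph**, on opioid use: "The mean, standard deviation, median, and interquartile ranges of narcotic usage (in morphine equivalent units) will be reported for each group". The next sentence adds: "The difference of narcotic usage between the two groups will be reported as a single value".
- **Hypothesis/Aims**: Aim 1 begins "To demonstrate decreased postoperative opioid usage" and goes on to pain scores. The second aim reads "Aim 2: To demonstrate decreased intraoperative opioid usage in the treatment group compared to controls". The title makes the same claim.
- **Study Population**: "A total of 150 patients is proposed for this study". The Procedures text sets 1:1 allocation, so 75 per arm.

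No confidence interval is mentioned anywhere in the document.

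**The concern.** Lower opioid use is what the trial sets out to show, and the amount is a continuous measurement. Logistic regression needs a categorical response. Sorted by outcome type, the plan therefore gives its main comparison a method that does not fit, while the t-test, which could be applied to an amount, is assigned to categorical variables.

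The effect measure is open as well. Each arm is to be summarised by both mean and median, and the difference is then a single unspecified number. In skewed data the difference in means and the difference in medians can be far apart.

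What is at stake is prespecification. If neither the test nor the estimate is fixed, both can be chosen after the data are seen, and a reader of the results could not tell whether they had been.

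**Working it through.** **1. The text against the variable types.** Three readings of the two method sentences are possible.

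| Reading | Method for opioid amount by arm | Method for non-normal amounts |
|---|---|---|
| By outcome type (ordinary reading) | Logistic regression: does not apply | None named |
| By predictor type (arm is a categorical predictor) | Two-sample t-test | None named |
| Labels swapped by mistake | Two-sample t-test (chi-squared would not apply) | None named |

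The general phrase on normal and non-normal data shows that a comparison is intended, but it does not fill the last column.

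**2. Inputs for size.** From the document: 150 patients, 1:1, hence 75 per arm, and a 0.05 threshold (two-sided is assumed). The 150 cannot be reproduced, because no effect size, SD or power is stated. It is used here only as the sample size. Assumed, because the document gives no distribution: log-normal opioid use, control median 60 morphine equivalents, a true 30% reduction (treated median 42), and log-SD s of 0.6, 0.8 or 1.0, with 0.3 added for mild skew.

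**3. Does the choice of test matter?** Simulation, 10,000 trials per setting:

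| | s = 0.6 | s = 0.8 | s = 1.0 |
|---|---|---|---|
| Power, t-test on raw amounts | 91% | 64% | 41% |
| Power, Wilcoxon | 94% | 75% | 55% |
| Power, t-test on logs | 95% | 77% | 58% |
| Raw t-test and Wilcoxon disagree on significance | 6% | 19% | 26% |
| Type I error, raw t-test | 4.9% | 4.7% | 4.5% |
| Type I error, Wilcoxon | 4.8% | 5.1% | 5.0% |

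At s = 0.3 the disagreement is about 0%, because both tests detect the effect almost every time.

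If the general phrase is taken to mean Wilcoxon whenever a Shapiro-Wilk test rejects normality in either arm (an assumed rule), normality is rejected in 100% of trials at these three log-SDs. Type I error and power then equal those of Wilcoxon.

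**4. Does the choice of difference matter?** The same true effect gives:

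| | s = 0.6 | s = 0.8 | s = 1.0 |
|---|---|---|---|
| Means: 60 × exp(s²/2) × (0.7 − 1) | −21.5 | −24.8 | −29.7 |
| Medians: 42 − 60 | −18 | −18 | −18 |
| Hodges-Lehmann shift (median of treated minus control) | −16.5 | −15.5 | −14.4 |

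**5. The omitted interval.** The half-width for the mean difference is t(0.975, 148) × √((SD₁² + SD₂²)/75), with t = 1.976. At s = 1.0 the SDs are 129.7 and 90.8, so 1.976 × √((129.7² + 90.8²)/75) = 36.1. An interval centred on −29.7 runs from −65.8 to +6.4. At s = 0.6 and 0.8 the half-widths are 13.2 and 21.8.

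**6. The t-test on categories (minor).** For a two-level variable at 30% in both arms, the t-test and chi-squared never disagreed in 10,000 runs. For a nominal variable with more levels, such as race, recorded in four groups, the t-test depends on arbitrary codes. With invented counts of 50/12/5/8 against 50/5/12/8, chi-squared gives p = 0.12, while the t-test gives 0.03 to 0.59 over the 24 possible codings.

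**The case against.** The strongest reply is that both sentences may sort explanatory variables rather than outcomes. Arm is a categorical factor, so a t-test would serve continuous outcomes and chi-squared categorical ones. Logistic regression would then relate continuous factors such as age or BMI to binary outcomes such as atrial fibrillation. The wording about variables and postoperative outcomes lends this some support, and it makes the paragraph coherent. This stands as a possible reading, so a reader should not infer that the plan contains no usable test under any reading. It does not close the gap: the text does not establish this reading, and no test for non-normal amounts is named under it.

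Three further replies have force.

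- **Error rate.** A reader might infer that the vagueness inflates false positives. The calculations do not support that: each test holds about 5%, and so does the assumed normality-gated rule.
- **Hidden uncertainty.** A reader might infer that reporting one number conceals the imprecision. It does so only in part, because the planned p-value and the per-arm SDs would let a reader recover much of it for a difference in means. The undefined contrast is the stronger half of that point.
- **Size.** The figures rest wholly on assumed skew. At a log-SD of 0.3 the two tests agree in practically every trial, and at 0.5 a separate run gave 99% power for both. The 19% and 26% apply only if the skew is marked.

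**Conclusion.** The point holds as a fault in the written rule. Under the ordinary reading, the one method named for continuous outcomes cannot compare opioid amount between arms. Under the more generous readings the plan offers at most a t-test, and nothing for the non-normal data it anticipates. The between-arm difference is undefined and has no interval. Because this is the title outcome and the subject of Aims 1 and 2, it should be corrected before any comparison by arm is made.

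The numerical consequence is conditional. With log-normal data, a 30% reduction and 75 per arm, disagreement between the raw t-test and Wilcoxon ranges from about 0% at log-SD 0.3 to about 25% at 1.0. Over log-SD 0.6 to 1.0 the candidate differences range from −14.4 to −29.7 morphine equivalents. The documents give no skewness, so they do not show where in that range the trial lies. The sentence may be a drafting slip, but the text does not show which test was meant. The use of a t-test for multi-level categorical variables is a side issue, since those named are descriptive, and chi-squared is correctly placed.

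**What to change.** **Data Analytic Methods, closing paragraph.** Keep the general sentence on comparative statistics, adding that the 0.05 threshold is two-sided. It is the only generic wording that reaches pain scores, which Aim 1 names, and times to events. Replace the two method sentences that follow it with:

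> Opioid amount in morphine equivalents will be compared between arms by the Wilcoxon rank-sum test, whatever its observed distribution, separately for postoperative use up to 72 hours and for intraoperative use. Other continuous outcomes, such as lengths of stay and spirometry volumes, will be compared by the same test. Categorical variables will be compared by the chi-squared test, or by Fisher's exact test where expected counts are small. Logistic regression will be used only for binary outcomes.

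**Data Analytic Methods, opening paragraph.** In place of the single unspecified value, state that the difference will be reported as the Hodges-Lehmann shift with its 95% confidence interval. This is neither the difference in means nor the difference in medians.

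Wilcoxon is one acceptable choice. A t-test on the log scale, with the ratio of geometric means and its 95% confidence interval, is equally acceptable if the handling of zero amounts is stated. What matters is one valid test and its matching estimate, named in advance.

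**Cost.** Two sentences replaced, one phrase changed and the sidedness added. No new patients or data are needed, since intraoperative and postoperative opioid amounts are already to be recorded.

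### The full/mini sternotomy analysis is optional, with no stated threshold, and takes each type on its own without an interaction test, so it cannot show whether the effect differs by type

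*Combined protocol and SAP*

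**What the plan says.** The combined protocol and SAP has one sentence on this analysis, at the end of Data Analytic Methods: "Depending on the enrollment rate, the stratification of data based on the type of sternotomy (full or mini) could be performed and analyzed respectively". The sentence before the named tests sets the only decision criterion, "with comparative statistics for normally and non-normally distributed data with $p < 0.05$ considered as significant". No interaction test, multiplicity adjustment, minimum group size or exploratory label appears anywhere.

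The hypothesis treats the two incision types as one population: "for patients undergoing upper mini- and median sternotomy compared to controls". Eligibility does the same, admitting anyone "undergoing a surgical procedure through mini- or full sternotomy". The main comparison is also pooled: "The difference of narcotic usage between the two groups will be reported as a single value".

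On size and allocation, Study Population says "A total of 150 patients is proposed for this study", and Procedures says "Qualified patients will be randomized 1:1 to a liposomal bupivacaine sternal block or a normal saline block". The list is made as follows: "An unblinded research coordinator will use a password-protected spreadsheet to randomly generate the subject's randomization assignment". Stratification of the randomization by sternotomy type is not mentioned.

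**The concern.** Two features of the sentence cause trouble.

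- **The analysis is optional and its trigger is undefined.** Without a threshold or a decision date, a reader of the final report cannot tell whether the split was planned at that enrollment or chosen later.
- **Each type is analysed alone.** A p-value below 0.05 in one type and above it in the other says little about whether the effects differ. The smaller group may simply have too few patients. The quantity that answers the question is the difference between the two within-type effects, and the plan does not estimate it.

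At stake is a subgroup conclusion about where the block is useful, drawn from a contrast that unequal group sizes alone can produce. The pooled comparison is not invalidated.

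**Working it through.** **Inputs from the documents.** 150 patients, 1:1, so 75 per arm; significance at p < 0.05.

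**Inputs assumed, because the documents do not give them.** Two-sided testing; no dropout; equal arms within each type; the same true standardized effect d (difference divided by SD) in both types; d from 0.3 to 1.0; mini patients from 75 (half) down to 15 (one tenth). The plan gives no power figure, so the 150 cannot be reproduced. Working backwards with a two-sample t-test, 75 per arm gives 80% power at d = 0.46 (0.4605).

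**Step 1: power within each type.** Noncentral-t power with n per arm in that type, 2n − 2 degrees of freedom and noncentrality d√(n/2). Half-patients are treated as continuous.

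**Step 2: exactly one type significant.** The two types contain different patients, so the tests are independent:

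P(exactly one) = pF(1 − pM) + pM(1 − pF)

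For 120 full and 30 mini at d = 0.4605, pF = 0.706 (60 per arm) and pM = 0.230 (15 per arm):

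- full only: 0.706 × 0.770 = 0.544
- mini only: 0.230 × 0.294 = 0.068
- exactly one: 0.544 + 0.068 = 0.61

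Other splits at d = 0.4605:

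| Mini patients | Power, full | Power, mini | Exactly one significant |
|---|---|---|---|
| 75 | 50% | 50% | 50% |
| 60 | 58% | 42% | 51% |
| 45 | 65% | 33% | 55% |
| 30 | 71% | 23% | 61% |
| 15 | 76% | 13% | 69% |

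**Step 3: other effect sizes, same method.**

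| d | 75 mini | 30 mini | 15 mini |
|---|---|---|---|
| 0.3 | 37% | 40% | 42% |
| 0.8 | 13% | 44% | 70% |
| 1.0 | 2% | 25% | 57% |

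**Step 4: no effect in either type.** At least one false positive from the two tests: 1 − 0.95² = 9.75%. Counting the pooled test as well, simulation gives about 11%.

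**Step 5: the interaction test.** When the effect is the same in both types, it falsely claims a difference 5% of the time at any split. Its power is limited. If d = 0.4605 in one type and 0 in the other, the standard error of the difference in SD units is √(2/nF + 2/nM) and power is about Φ(d/SE − 1.96):

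- 75 mini: SE = √(2/37.5 + 2/37.5) = 0.327; Φ(1.410 − 1.96) = 29%
- 30 mini: SE = √(2/60 + 2/15) = 0.408; Φ(1.128 − 1.96) = 20%

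**The case against.** The strongest reply is that the harm is inferred. The sentence does not say that within-type p-values will be compared, or that the block will be declared effective in one type and not the other. Within-type estimates with intervals would also satisfy it. That is correct. What stands is that p < 0.05 is the plan's only criterion and nothing provides a proper comparison between types.

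A reader might also infer that the trigger lets results drive the choice. The documents do not support that: enrollment rate is not outcome data. The condition may even be meant to skip the split when one type is rare, which would remove the most uneven rows in the tables. The fair criticism is that no threshold is stated, so neither the intention nor its timing can be checked.

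A third tempting reading is that the split would usually produce a discordant result. That depends on the effect and the mix, neither of which is given. With a large effect and an even split, discordance is about 2%.

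The added false-positive risk is real but small beside the rest of the plan, which applies the same threshold to 11 postoperative variables, one of them pain at ten time points, and names no primary outcome. Nothing in the documents shows that sternotomy type predicts opioid use, so no precision gain from adjustment can be counted on.

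**Conclusion.** The point holds in a limited form. The plan leaves the sternotomy analysis optional on an undefined trigger, and when it is done each type is analysed alone with no estimate of the difference between types.

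With a common effect in 150 patients, the chance that exactly one type reaches p < 0.05 runs from about 2% (d = 1.0, even split) to about 70% (d = 0.8, 15 mini patients). At the effect that gives 80% overall power it is at least 50% for every split examined. These figures rest on the assumed effect, split, two-sided testing and equal arms within type. They show what separate testing can do; they do not predict what this trial will report.

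This should be corrected before analysis, but it does not threaten the pooled comparison.

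**What to change.** Replace the sentence with:

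> Sternotomy type (full or mini, as planned before surgery) will be recorded for every patient and included as a covariate in a linear model (on a suitable scale) comparing opioid use between arms in all patients, regardless of enrollment rate. As an exploratory analysis, the treatment-by-type interaction will be reported with its 95% CI, and within-type estimates will be shown with CIs and no separate significance claims. A non-significant interaction will not be taken as evidence that the effect is the same.

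The cost is small but not zero.

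- **One explicit data field.** The data elements list the type of procedure, which may mean the operation and not the incision. Sternotomy type is part of eligibility, so it is known for every patient.
- **A little more modelling.** The plan names t-tests, chi-squared tests and logistic regression, so the linear model has to be added.
- **An imprecise interaction estimate.** Power is about 20-29% if an effect of d = 0.46 exists in only one type (30 to 75 mini patients), so no firm subgroup conclusion should be expected.

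No extra patients or visits are needed.
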